participating research studies. All subjects will receive standard text messages and will be randomized to one of four groups (blocked within each study to ensure balanced groups): (1) Standard recruitment (SR): subjects will receive text messages ~2 days prior to their Intake visit with relevant information about the time, date, and location of the visit as well as contact information for study staff ("You have a study visit on [Date] at [Time]. Visit comp is \$10. Reply Y to confirm. See <http://j.mp/2222222> for reminders. Reply or appt may be canceled."); (2) SR + Information Provision (IP): Subjects will receive personalized messages designed to target injunctive norms regarding participating in research (e.g., "[Name], wondering why you should volunteer for research? Many find it a rewarding way to advance science and be a part of a community <http://j.mp/2222222>."); (3) SR + Contingency Management (CM): CM will be provided in the form of an opaque "lottery jar" with a high proportion of chips with little (\$1) monetary value. Participants draw from the lottery jar upon completion of an objectively verified target behavior (e.g., attending an Intake visit), and bonuses are often provided for continued performance [74, 75]. This strategy has been successful in augmenting visit compliance in several treatment studies [80-82]. All text reminders will be delivered using the Way 2 Health (W2H) software platform. Upon completion of all requirements for a given visit, participants will receive 5 lottery jar draws for that visit. Attendance at all visits earns participants bonus draws upon completion of the study. Failure to attend a visit without prior approval or failure to complete all visit requirements results in no draws for that visit. The lottery jar contains 500 chips: 250 say "good job," 219 have a value of \$1, 30 have a value of \$5, and 1 has a value of \$100. The study completion bonus will be 5 extra draws. Thus, at each visit, subjects will have the opportunity to make 5 draws from the lottery jar, for maximum possible earnings of \$120; (4) SR + IP + CM (IC): In this group, subjects will receive the targeted text messages and receive CM. The design of our study allows us to examine each strategy independently as well as combined to evaluate the optimal approach.

3. Study Duration

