Salivary testosterone: Salivary testosterone will be used to control for between-session differences that may occur due to change in testosterone levels in male and female participants. Testosterone (pg/ml) will be collected at the start of the scan session. Approximately 2 ml of saliva will be collected using a passive drool method and saliva collection aid (Salivette LLC, State College, PA, USA). The saliva will be stored in plastic vials at –20°C. Saliva samples will be assayed using testosterone EIA kits (Salimetrics LLC, State Collect, PA, USA). Salivary testosterone is highly correlated with plasma testosterone [55].

fMRI Measures: See fMRI Scanning Sessions above.

Primary Outcomes (Main Study): Multiple measures of abstinence will be measured for this study. The primary outcome will be the number of days to relapse following the target quit date. Relapse will be confirmed using a conventional SRNT guideline criterion of either a positive biochemical verification of smoking [3, 56] or 7 consecutive days of smoking based on self-report (it is very unlikely that a subject would meet the latter criterion without also meeting the former, given the long half-life of cotinine). The days to relapse will be based upon time from target quit date to the first day of the relapse period. Self-reported daily smoking data will be collected using a validated timeline follow-back method [57]. Self-reported abstinence will be biochemically verified on a weekly basis using urine cotinine (<100ng/ml) [56] and a CO reading

of ≤5PPM. Drop-outs will be considered relapsers following the last date of abstinence data provided [7, 58]. Secondary outcomes will include days to first “slip”, and cross-sectional measures of 7-day and 30-day point prevalence (biochemically verified weekly with cotinine, which provides an assessment of smoking in the last 7 days).

Carbon Monoxide (CO): The CO monitor is a handheld device that uses a disposable mouthpiece, reports CO in parts per million (ppm), and takes about 5 minutes to administer. Carbon monoxide measurements will be collected from smokers at each visit as a biochemical verification of smoking exposure.

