Data Screening: Prior to performing analyses, standard data screening/cleaning procedures will be applied. These procedures will (a) screen the data for data-entry errors, (b) check for outliers, (c) assess the extent and pattern of missing data, (d) create all summary scores needed for analysis, and (e) check that appropriate distributional assumptions are met. Assumptions will be examined using standardized residuals, influence diagnostics, and graphical displays. We will employ image quality assessment procedures to examine global and ROI-based raw and processed temporal signal-to-noise ratio, absolute and relative motion, and signal spike count. Subjects with potential outliers (>2 SDs above mean) will be flagged to determine if the time-series is valid, and if so it will remain. Otherwise it will be corrected or removed from the analysis. The final sample will be examined in a similar fashion to determine whether any subjects warrant data cleaning or exclusion from the final analysis. All analyses will be conducted using Stata software (STATA Corporation, College Station, Texas).

Missing Values: We will examine the characteristics of those subjects who drop out to identify any associations between dropout and baseline measures. These analyses will be descriptive, as we expect few dropouts. Items missing at random on survey measures will be imputed prior to calculating final scores using conditional means, estimated with a version of Buck’s method [65]. The analyses will also be repeated using only complete observations to assure that parameter estimates are not impacted by imputation.

Task fMRI: fMRI preprocessing will use standard algorithms in FSL (FMRIB’s Software Library, www.fmrib.ox.ac.uk/fsl) including distortion correction, slice-time correction, motion correction, spatial smoothing, high-pass filtering (120s) and co-registration to the MPRAGE. fMRI preprocessing will also include removal of physiological noise related to in-scanner pulse and respiration measures using RETROICOR. After preprocessing, basic subject-level BOLD time series analysis will be carried out using the general linear model (GLM) in FSL, using a canonical double-gamma hemodynamic response function (HRF) for convolution, and linear contrasts to estimate task-specific BOLD responses for each individual. Temporal derivative and extended motion parameters will be included in models when appropriate. For the block-design

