N-back task, analysis will focus on the parametric effect of increasing working memory load across four levels (linearly modeled [-3 -1 1 3]). For the cue reactivity task, the primary contrast will be smoking cues>neutral cues. For the stress task, the primary contrast will be stress > control blocks.

Subject-level statistical image maps will be transformed into a common anatomic space (Montreal Neurological Institute, MNI) for group-level analysis. Session (abstinence vs. smoking) whole brain, voxelwise analyses will test abstinence effects in brain regions specified above. The peak voxel in each significant cluster will be used to assign appropriate anatomical labels. Percent signal change within significant clusters will be utilized in regression models described below. Age, self-reported ethnicity, nicotine dependence severity (FTND), and withdrawal symptom severity will be included as covariates in the relevant statistical models. For all tests, significance will be determined using cluster $p < .05$ and voxel-height $Z > 2.33$.

Aim 1: Modeling of Days to Relapse:

The outcome associated with Aim 1 is censored time to event and the predictors are continuous measures (difference scores) extracted from ROIs associated with each neurobehavioral domain. We will test this hypothesis within each domain (working memory, cue reactivity, and stress) using Cox regression; the test statistic will be the z-score corresponding to the hazard ratio, with significance corrected for the total (8) cross domain ROIs. We will also test baseline clinical predictors and abstinence challenge-related performance measures (difference scores) for entry into each of the domain specific models.

Aim 2: Integrated Brain-Behavior Model:

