Participants will be eligible for compensation only if they complete the visits/assessments listed below (Table 3). Participants who are found ineligible for any reason during Study Visits will only be provided \$10 for their time, in addition to their preferred travel coverage for that session. Participants who withdraw partway through a session (other than the Intake session) may receive prorated compensation for that session. Through participation in this research study participants are estimated to earn up to \$810 in visit compensation. If the participant elects to use the ride service, all travel will be paid for by the research study. If the participant elects to travel to and from their appointments independently, they will be reimbursed \$10/visit (\$120 over the course of the study) to put towards their travel expenses.

Recruitment and Retention Pilot: Upon completion of all requirements for a given visit, participants randomized to CM will receive 5 lottery jar draws for that visit. Attendance at all visits earns participants bonus draws upon completion of the study. Failure to attend a visit without prior approval or failure to complete all visit requirements results in no draws for that visit. The lottery jar contains 500 chips: 250 say “good job,” 219 have a value of \$1, 30 have a value of \$5, and 1 has a value of \$100. The study completion bonus will be 5 extra draws. Thus, at each visit, subjects will have the opportunity to make 5 draws from the lottery jar, for maximum possible earnings of \$120 per visit.

Participants will be paid in cash for intake visits. At the baseline visit participants will be issued a Greenphire ClinCard, which is a reloadable, pre-paid card for the purposes of compensation. Compensation will be loaded onto the ClinCard at the end of successfully completed visits. Participants may opt to receive a text message alert when a payment has been loaded onto the ClinCard.

TRAVELING VIA THE RIDE SERVICE

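### The Aim 1 and Aim 2 Cox models leave out the pilot arm, although contingency management rewards attending the visits that record relapse: a minor, nearly free improvement

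*Combined protocol and SAP*

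**What the plan says.** **Pilot.** Study Design lists 824061 as one of four studies feeding the pilot: "All subjects will receive standard text messages and will be randomized to one of four groups". Two of the four groups receive CM. Under Subject Compensation, on completing a visit "participants randomized to CM will receive 5 lottery jar draws for that visit", and "Failure to attend a visit without prior approval or failure to complete all visit requirements results in no draws for that visit". Table 3 shows 5 draws at Intake, each scan, Pre-Quit, the target quit date and Monitoring Visits 1–4, up to 10 at Monitoring Visit 5, and none at the 6- and 12-month contacts.

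**Endpoint.** Primary Outcomes (Main Study) defines days to relapse and states: "Self-reported abstinence will be biochemically verified on a weekly basis using urine cotinine". It adds: "Drop-outs will be considered relapsers following the last date of abstinence data provided". Missing Values says of the drop-out comparisons: "These analyses will be descriptive, as we expect few dropouts".

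**Model.** Aim 1 uses Cox regression on ROI difference scores within each domain. Task fMRI names age, ethnicity, FTND and withdrawal severity as covariates. Aim 1 adds: "We will also test baseline clinical predictors and abstinence challenge-related performance measures". Aim 2 builds interaction models on the same outcome. Pilot arm appears nowhere in these sections. The one sentence about a term for all models stands under the pilot's secondary outcomes and names the individual study, not the arm.

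**The concern.** CM pays for turning up at the visits where abstinence is verified, and drop-outs are coded as relapse. The protocol itself expects CM to improve attendance. A randomised factor recorded for every pilot participant may therefore shift the recorded event time, and the primary model ignores it.

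Two things could be at stake.

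- **Power.** Hazard ratios are not collapsible. Leaving out a prognostic factor pulls the ROI hazard ratio towards 1 even when the factor is independent of the ROI score, and the stated power of 80% leaves little slack.
- **Comparability.** Pilot texts start before Intake, and draws also reward Intake and both scans, so CM could affect who ends up in the scanned sample. Being in the pilot is itself not randomised: it needs an SMS-capable phone and consent to texts, while people without either may still join the main study.

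**Working it through.** **1. The plan's own power figure.** Inputs from Power and Sample Size Considerations: n = 200, alpha 0.0085, d = 0.25 or HR 1.32, power 80%. Sidedness is not stated; two-sided fits.
- One-sample test: power = Φ(0.25 × √200 − 2.632) = 0.817 (0.809 with the noncentral t). This reproduces 80%.
- Events for HR 1.32 per SD: (2.632 + 0.842)² / (ln 1.32)² = about 157, or 78% of 200. The plan gives no event count.

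**2. Size of the incentive.** "The lottery jar contains 500 chips": 250 pay nothing, 219 pay $1, 30 pay $5 and 1 pays $100.
- Expected value per draw: (219 × 1 + 30 × 5 + 1 × 100)/500 = $0.938, so $4.69 for 5 draws.
- Target quit date to Monitoring Visit 5: 5 × 5 + 10 = 35 draws, worth 35 × 0.938 = $32.83. Over the same visits Table 3 offers $70 visit pay, up to $300 for verified abstinence and a $50 attendance bonus.

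**3. Share exposed (assumption).** With an equal split of about 576 across four studies, 144 fall to this study and 72 receive CM. At enrolment of 28% (the plan's standard-arm rate) to 40% (28% plus the 12-point target difference), 20 to 29 enrol: 10–14% of 200. If the whole sample were in the pilot, the share would be about half.

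**4. Size of the arm effect (assumption).** If CM works only by halving drop-out, and drop-outs are 20% of recorded events, the overall hazard multiplier is about 0.8 + 0.2 × 0.5 = 0.9. At 40% of events it is 0.6 + 0.4 × 0.5 = 0.8. A multiplier of 0.5 would need CM to change smoking as well.

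**5. Simulated power for the ROI test.** n = 200, 78% events, HR 1.32 per SD, two-sided alpha 0.0085; 1,500 or 4,000 replicates, so each figure has a standard error of about 1.1 or 0.7 points.

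| On CM | Hazard multiplier | Arm omitted | Arm included |
|---|---|---|---|
| 50% | 1.0 | 80.2% | 79.7% |
| 50% | 0.9 | 78.0% | 77.9% |
| 50% | 0.8 | 76.9% | 78.0% |
| 50% | 0.7 | 75.9% | 76.9% |
| 50% | 0.5 | 72.0% | 78.0% |
| 12% | 0.9 | 77.5% | 77.7% |
| 12% | 0.8 | 78.6% | 78.5% |
| 12% | 0.67 | 77.2% | 78.1% |
| 12% | 0.5 | 74.7% | 77.6% |
| 14% | 0.5 | 74.9% | 78.2% |

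Other runs of the 50%, 0.5 case gave 70% against 77% or 78%. A multiplier of 0.3 gives 55% against 77%, but nothing in the documents points to an effect of that size.

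**6. Type I error (nominal 0.0085).**
- Arm independent of the ROI score, half on CM: 0.0085 (multiplier 0.5) and 0.008 (0.3) with arm omitted.
- Arm and ROI score correlated (assumed), multiplier 0.5, half on CM: 0.014 at r = 0.1 and 0.034 at r = 0.2 with arm omitted; 0.008 and 0.006 when stratified.
- r = 0.1 with multiplier 0.7: 0.009 with arm omitted.

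**The case against.** The case for leaving the plan alone is strong.

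- **No validity problem is shown.** Arm is randomised and the draws reward attendance, not abstinence. A reader might infer that the omission confounds the ROI association or inflates false positives. Step 6 shows that it does not, unless arm and ROI score are correlated, and the documents show no such correlation. This stands.
- **The large power loss needs extreme inputs.** A reader might take a drop to about 70% as the expected cost. It needs CM to halve the whole hazard in half the sample, while the plan expects few drop-outs and the draws are small beside the other payments. Enrolment began in June 2016 and a pilot reference carries a May 2017 access date, which suggests that early participants may predate the pilot. This also stands.
- **A missed visit is not a relapse.** The rule concerns drop-outs. Telephone assessment may cover a missed visit at the investigator's discretion, and timeline follow-back records daily smoking. Better attendance could also detect more smoking, so even the direction of the CM effect is unknown.
- **A covariate does not remove attendance-driven events.** Drop-outs remain coded as relapse whatever the model contains. This is right, and the fix allows for it.

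Randomisation does not cover two points: selection into the scanned sample after randomisation, and pilot participation, which was never randomised. Neither is shown to matter here, but both are possible.

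**Conclusion.** The point holds as a minor, free improvement. Recorded time to relapse may depend on pilot arm through attendance, and the Aim 1 and Aim 2 Cox models do not allow for it. The documents do not support calling this a bias or a type I error problem: bias would arise only if arm or pilot participation is linked to ROI scores among those scanned.

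The expected loss is about 0–1 points of power if CM acts only through drop-out. With 12–14% of the 200 on CM it is about 1 point at a multiplier of 0.67 and about 3 points if CM halves the total hazard. It is 6–8 points only if CM halves the total hazard with half the sample on CM. These figures rest on assumed CM effects and exposed shares, neither of which the documents give, and on the 78% event rate implied by HR 1.32. They concern the Aim 1 main effects; the Aim 2 interactions were not simulated.

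**What to change.** 1. Pre-specify pilot status in three levels (not in pilot, pilot without CM, pilot with CM) as a stratum or covariate in every Aim 1 and Aim 2 Cox model.
2. Report drop-out, and the share of relapse events that come from the drop-out rule, by pilot status.
3. Add a sensitivity analysis that censors drop-outs at their last abstinence data. It should stay a sensitivity analysis, because censoring assumes that drop-outs have the same relapse risk as those who remain.
4. Reconcile Table 3 and its footnote 7, which list draws without limiting them to CM arms, with the pilot design and compensation text, which do limit them. The arm contrast depends on this.

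Cost: SAP wording only. Arm is already recorded. A three-level covariate adds two parameters against about 157 implied events, and in the simulated scenarios including arm never lowered power by more than simulation noise.

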- [name], Support Staff
- [name], Support Staff

2. Staff Training

[name] and the Project Managers will oversee the development of protocols for laboratory related tasks and training of staff in these protocols. [name] and/or the Project Managers will be responsible for the development of procedures pertaining to all study visits and implementing and monitoring ongoing staff training procedures accordingly. An initial, intensive training period will be implemented followed by periodic in-service trainings that will be coordinated by the Project Managers. They will also oversee study progress as part of regular study meetings. All research staff will undergo training on research practices involving human subjects, including the protection of subject confidentiality, and will maintain current certification in patient oriented research.

3. Study Facilities

This project will be conducted at and through the Center for Interdisciplinary Research on Nicotine Addiction (CIRNA) at the University of Pennsylvania. The above mentioned center has numerous similar protocols and well-developed procedures for staff training, data collection and

storage, and study completion. The facilities available for this project include a large conference room, individual consulting rooms with computer/internet access, storage rooms, office space for study personnel, and data management facilities. The Magnetic Resonance Imaging Center in the University of Pennsylvania Medical Center provides all the necessary equipment and staff to conduct an fMRI investigation.

References

1. Ahnallen, C.G. and J.W. Tidey, *Personalized smoking environment cue reactivity in smokers with schizophrenia and controls: a pilot study*. Psychiatry Res, 2011. **188**(2): p. 286-8.
2. Schnoll, R.A. and C. Lerman, *Current and emerging pharmacotherapies for treating tobacco dependence*. Expert Opin Emerg Drugs, 2006. **11**(3): p. 429-44.
3. Hughes, J.R., J. Keely, and S. Naud, *Shape of the relapse curve and long-term abstinence among untreated smokers*. Addiction, 2004. **99**(1): p. 29-38.
4. Piasecki, T.M., *Relapse to smoking*. Clin Psychol Rev, 2006. **26**(2): p. 196-215.
5. Niaura, R., et al., *Symptoms of depression and survival experience among three samples of smokers trying to quit*. Psychol Addict Behav, 2001. **15**(1): p. 13-7.
6. Lerman, C., et al., *Translational research in medication development for nicotine dependence*. Nat Rev Drug Discov, 2007. **6**(9): p. 746-62.
